We will conduct additional exploratory analyses using the stratification factors (age, sex, and antihypertensive use) as covariates. As uncertainty exists on the distribution of enrolled participants within these strata (e.g. young men taking antihypertensive medication), we cannot estimate the preliminary statistical power for these exploratory aims. Thus, we will estimate the power based on the strata sizes prior to conducting the exploratory analyses. Interaction terms (e.g. age with behavioral interventions, sex with behavioral interventions, etc.) will be utilized to determine if specific groups respond well to specific intervention elements. Baseline BP may also play an important role. We will examine its impact by dividing the cohort into tertiles. We will repeat the above primary and exploratory modeling within each of the three initial BP strata to determine if there is heterogeneity of effect (e.g. do patients with the highest baseline BPs get the most benefit from the intervention components?). We will similarly assess the impact of the intervention components on the exploratory and process outcomes using linear, Poisson, logistic, or ordinal regression depending on the distributions. In addition, we will conduct longitudinal analyses that include all BP measurements over time (including those by text and at the in-person visits) to assess the temporal profiles of response in the intervention components.

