9.3 Sample Size and Accrual

We originally planned to enroll approximately 960 patients into the eligibility phase. From this group, we estimate that 480 participants will report qualifying BPs and will be randomized to one of the eight intervention arms. We anticipate 240 participants will fully complete the 12 month, in person follow up visits.

However, after accruing approximately 400 randomized participants, we noted lower than expected retention at 6 month visits. Therefore, we will adjust the maximum total number of enrollments and randomizations upwards by 50% each. The overall intention is to achieve approximately 240 protocol completers (attendees at 12-month visit). We will continue to monitor accrual and retention in order to achieve this target.

In the work by Collins and others, methods for sample size estimations for factorial design, MOST based interventions, have previously been reported. It is important to note, that the primary hypotheses driven by these designs is not in the pairwise comparisons of each of the interventions, but instead is the overall estimate of the effects of each of the individual intervention components, and their combinations. This smallest standardized effect size of 0.35 corresponds to a BP change of 1 mm Hg and standard deviation of 2.8 mm Hg for each parameter. We believe this is the minimal clinically significant change for each component; and to achieve improvements of 3-4 mm Hg over the course of a year, our chosen regimen for the next phase

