Sample Size: We plan to enroll approximately 960 patients into the eligibility phase. From this group, we estimate that 480 subjects will report qualifying BPs and will be randomized to one of the eight intervention arms. We anticipate 240 subjects will fully complete the 12 month, in person follow up visit. For 80% power to detect the smallest main expected effect of 0.35 based on the Collins method of a 3-factor experiment analyzed using a second order model (i.e. main effects and 2-way interactions), we require 196 subjects. Assuming 480 randomized subjects and allowing an additional 50% loss to follow up after the eligibility phase, we expect at

least 240 subjects, exceeding 80% power with an alpha level of 0.10 (inflated to reduce likelihood of dismissing active components with modest BP reducing effect) – we used the FactorialPowerPlan SAS macro to calculate power. For the secondary analyses, considering an alpha of 0.05 and a baseline proportion attending 2 or more primary care provider visits within one year of 40%, with a total sample size of 240 evenly distributed between the active appointment scheduling and passive appointment, we have 87% power to detect an increase to 60% attending 2 or more visits. The time to event analysis (considering an alpha of 0.05, power of 99%, and 240 subjects enrolled over 720 days, followed for 30 days) can detect a change from 20% of subjects in the non-facilitated group to 20.4% of subjects in the facilitated group.

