Analysis Plan: The primary analysis (aim 1) will fit a linear regression model with the outcome of SBP change (baseline minus 12 months) and main effect-coded binary predictors of healthy behavior texts (yes vs. no), prompted BP self-monitoring frequency (high vs. low), and primary care provider visit scheduling and transportation (active vs. passive). Initial analyses will focus on the main effects. Additional analyses will include all the two-way interactions of the three intervention components (only considering interactions where at least one of the factors in the interaction demonstrates a sufficiently large main effect). As the goal of this exploratory trial is to find interventions and combinations with activity, we will use an alpha level of 0.10 for all main effects and 0.20 for interactions. We plan to include elements meeting that bar for statistical significance in the subsequent multicenter trial. If significant interactions exist (i.e. the combination of facilitated transportation and high frequency home BP monitoring), we plan to implement the combination of elements that has the highest expected reduction in SBP – assuming we achieve significance at the p=0.1 (main effects) or 0.2 (interaction) level for the components. In the event of an overall “null” trial, we would examine the expected change in SBP for arm 1, which would be represented by the intercept. If this was significantly greater than 0 at the p=0.1 level we would propose a very simple subsequent multi-center trial using only weekly prompted BP self-monitoring.

The main secondary analyses (aim 2) will use time-to event (Cox Proportional Hazards) and logistic regression. For the endpoint of interest, (either time to first primary care visit, or the binary variable indicating attendance at two or more primary care visits within 1 year of randomization), we will fit an adjusted regression model. The main predictor of interest for these models is assignment to the active primary care provider scheduling and transportation arm (50% of all subjects randomized in the trial), while adjusting for the assignment into other groups similar to aim 1 (healthy behavior text messages and prompted BP self-monitoring).

2. Analysis Plan

2.1 Preliminary evaluation of data:

Purpose: To identify issues that will affect our approach to the primary analysis. Specifically:

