2.4. Primary analysis/results

Purpose: Primary results for the intention to treat (ITT) analysis.

Methods/Approach:

Intention to Treat Dataset: all subjects randomized into study and all data observed from each subject regardless of compliance and adherence with the assigned intervention or follow-up.

Primary outcome: Change in systolic BP from baseline (median of three qualifying SBP from eligibility phase) to 12 months. Baseline minus 12 months.

Primary analysis: The primary analysis will fit a linear regression model with the outcome of SBP change and main effect-coded binary predictors of healthy behavior texts (yes vs. no), prompted BP self-monitoring frequency (high vs. low), and primary care provider visit scheduling and transportation (active vs. passive) and the stratification variables. Initial analyses will focus on the main effects. The outcome will be transformed (e.g., log) if necessary.

$$(BL\ BP - 12\ mo\ BP) = \beta_0 + \beta_1\ HBtexts + \beta_2\ HighBPmonitor + \beta_3\ PCPfacilitated + \beta_4\ female + \beta_5\ Age > 65 + \beta_6\ AHT + \beta_7\ Black$$

Where HBtexts= 1 for daily healthy behavior texts and 0 for none; HighBPmonitor=1 if daily BP monitoring and 0 for weekly; PCPfacilitated=1 for provider scheduling and transportation facilitated and 0 for not facilitated; female = 1 for self-reported female, 0 for male; Age>65=1 for Age \geq 65, 0 for 18-64; and AHT=1 for antihypertensives in the past 6 months, 0 for not; Black=1 for Black, 0 for Other

Missing data:

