We will work to prevent missing data by the recruitment and retention strategies described elsewhere. The amount and patterns of missing data and its associations with other variables (in particular intervention category) will be explored so that an appropriate statistical method for analysis can be used. If the data is missing at random (missing outcomes can be predicted from other observed variables, especially recent self-reported blood pressures), which we believe to be the most likely, since we obtain text messaging-based BPs at least weekly, the repeated measurements within individuals will allow us to use multiple imputation to handle sporadic missing at random BP measurements. For multiple imputation, we will use R package mice to impute the data using multiple imputation by chained equations. Non-normal continuous missing variables will be transformed for normality and back-transformed for any calculations necessary (e.g., change in BP). The imputation model will include all variables in the analysis model, treatment interactions, as well as other covariates that predict the missing variable and whether the missing variable is missing. Thus, associations between baseline variables and missing variables will be assessed both for strength of association and functional form. We will use 100*fraction of incomplete cases number of imputations. Analyses will combine regression estimates using Rubin's rules. Model checking will be performed on each imputed dataset through residual analysis to identify any issues with the imputation model or analysis model. Problems occurring in a small number of imputed datasets suggest a problem with the imputation dataset and problems occurring consistently across all imputed datasets suggest a problem with the analysis model.

In the case of non-ignorable missing (missing not at random) data, sensitivity analyses will be performed using pattern mixture or selection models to evaluate the robustness of our conclusions to a range of sensible conditions (for both the primary and additional analyses of the primary endpoint).

Interpretation:

Results will be reported as parameter estimates, 95% confidence intervals, and 2-sided p-values. As the goal of this exploratory trial is to find interventions and combinations with activity, we will use an alpha level of 0.10 for all main effects. Plots of mean BP levels over time will be generated for the 3 main effects and each intervention group.

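### The covariates in the primary model differ between Protocol 9.1, SAP Section 1 and SAP 2.4, and the null-trial rule that reads arm 1 from the intercept fits only the components-only version

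*SAP*

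**What the plan says.** Five places describe the primary model.

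- **Protocol 9.1 and SAP Section 1** give a linear regression of SBP change on the three components. In both, the predictor list ends without covariates: "primary care provider visit scheduling and transportation (active vs. passive). Initial analyses will focus on the main effects".
- **Protocol 9.1, next paragraph**: "We will conduct additional exploratory analyses using the stratification factors (age, sex, and antihypertensive use) as covariates".
- **SAP 2.4, sentence**: the list ends with "primary care provider visit scheduling and transportation (active vs. passive) and the stratification variables". Under SAP Section 1 and Protocol 5.3.5 these variables are age, sex and antihypertensive use.
- **SAP 2.4, equation**: a seventh coefficient is added, with "Black=1 for Black, 0 for Other". Race is not a stratification factor.
- **SAP 2.5a**: the longitudinal model takes over the three stratification variables and attributes them to the primary model, without race.

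The test is fixed: "we will use an alpha level of 0.10 for all main effects", with two-sided p-values. Within the SAP, only Section 1 says what follows from it. Components that pass go into the next multicentre trial. If none do, the arm 1 change is read from the intercept and tested at 0.10.

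**The concern.** Passing p<0.10 is what carries a component forward, so the model that produces the p-value should have one reading. Here the go-forward rule stands beside a model with no covariates, while the only written equation has four. The models share a treatment estimand but give different estimates and standard errors, so a component near the bar can pass under one and fail under another. Multiplicity is deliberately left uncontrolled (SAP 2.5c), so a single fixed model is one of the few constraints on the selection.

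The null-trial rule is also exposed. It equates the intercept with arm 1's expected change, and that equality depends on which covariates are in the model and how they are coded.

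**Working it through.** **1. The plan's sample size, and whether the covariates affect it.** Inputs: "For 80% power to detect the smallest main expected effect of 0.35" (SAP Section 1), alpha 0.10 two-sided, half of N at each level of a factor. Protocol 9.3 says the effect "corresponds to a BP change of 1 mm Hg and standard deviation of 2.8 mm Hg for each parameter", which is 1/2.8 = 0.357.

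N = 4(z₀.₉₅ + z₀.₈₀)²/d² = 4(1.645 + 0.842)²/d² ≈ 24.73/d²

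- d = 0.35: 24.73/0.1225 = 201.9
- d = 1/2.8: 24.73 × 7.84 = 193.9

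The stated 196 lies between these. Power at 196 is 79.0% (d = 0.35) or 80.4% (d = 1/2.8), and at 240 it is 85.7% (d = 0.35). A noncentral-t calculation gives 85.5% at 240 and moves by less than 0.1 point between 4 and 11 model parameters. The sample size is not in question.

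**2. How often the choice of model changes the selection.** The documents give no R² for the covariates, so it is assumed. The first two rows below use 240 completers, total R² 0–20%, and covariates left to chance balance among completers. The third row uses 480 randomised in stratified blocks of 8, random loss to 240, R² 0–20% for the strata plus 0–10% for race. It assumes 50% female, 12% aged 65 or over, 45% on antihypertensives and 57% Black. Entries are the share of trials in which at least one of the three components changes pass/fail at p<0.10.

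| Comparison | No effect | 0.2 SD | 0.35 SD |
|---|---|---|---|
| Components only vs 2.4 equation | 6–22% | 12–42% | 7–24% |
| 2.4 sentence vs 2.4 equation (race term only) | 2–11% | 4–22%* | 3–11% |
| Any difference among the three models | 5–27% | 11–52% | 6–28% |

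*From a separate run in which race carries a quarter of the explained variance.

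As a cross-check on the first row, the stratified-block run gives per-component disagreement between the components-only model and the equation, under no effect, of 1.4%, 4.0%, 5.8% and 7.9% at total R² 0, 7%, 15% and 30%. Three components give at most 3 × these: 4.2%, 12.0%, 17.4% and 23.7%. This is the same order, slightly lower because stratified blocks hold the strata closer to balance.

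**3. Error rate.** With one fixed model the level is 10% per component, and the chance of at least one false pass is 1 − 0.9³ = 27.1%. When the covariates are strongly prognostic the components-only model is slightly conservative (8.2% at the strongest setting).

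**4. The intercept.** SAP 2.4 codes every predictor 0/1. With components only, β₀ is the modelled arm 1 mean. Under the 2.4 equation,

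arm 1 mean = β₀ + β₄·p(female) + β₅·p(65 or over) + β₆·p(antihypertensive) + β₇·p(Black)

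so β₀ alone is the arm 1 change for non-Black men under 65 not on antihypertensives. With the prevalences above, and treating them as independent, that is 0.50 × 0.88 × 0.55 × 0.43 = 0.104, about 10% of participants. If effect coding in Section 1 means −1/+1, the components-only intercept is a grand mean and not arm 1 either.

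**The case against.** The SAP largely points to its own answer. Section 1 is headed as a review of the design and repeats protocol text, while Section 2 is the operative plan. Only 2.4 gives an equation and coding. SAP 2.5a adds the interactions to the primary model of Section 2.4, and 2.6 repeats that model in the baseline-BP tertiles. Race is adjusted for in 2.5b and 2.7, so its absence from the 2.4 sentence looks like an omission. Within SAP Section 2 the open question is one term. This stands, and it is why the 2.4 equation is the version to adopt.

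It can also be said that Protocol 9.1 never uses the word unadjusted, that its exploratory paragraph is mainly about subgroup response, and that the trial is declared exploratory. The first two soften the conflict but do not remove it: the protocol lists covariate use as additional, and version 14.0 postdates the SAP by almost four years without adopting its model. The exploratory status lowers the stakes, but the p<0.10 result still selects the components.

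A reader might infer that the model is to be chosen after unblinding, so that the best of three p-values is taken. On that reading, per-component error would be 10.8–14.6% and the chance of any false pass 29–37%. The documents do not support it. No passage plans such a choice. The SAP is dated September 2018, and recruitment began in 2019 (Protocol Appendix L). SAP 2.2 allows plan changes in light of how the study unfolded, but it lists flow and retention items, not covariates.

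**Conclusion.** The inconsistency is real and lies in current text. It is a consistency correction to the primary analysis, with no sign of intended model selection. Alignment matters most for borderline effects: between the components-only model and the 2.4 equation, the set of passing components differs in about 12–42% of trials at 0.2 SD, against 7–24% at the design effect of 0.35 SD and 6–22% under no effect. The race term alone accounts for about 2–11% under no effect and 3–11% at 0.35 SD. All of these rest on an assumed covariate R² of 0–20% and 240 completers; the low ends apply if the covariates explain nothing. The intercept problem needs no such assumption beyond the 0/1 coding in SAP 2.4: under that equation the null-trial rule tests a subgroup's change instead of arm 1's, unless the covariate terms happen to cancel.

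**What to change.** - Name the SAP 2.4 equation (three components, three stratification factors, race) as the only primary model.
- Add race to the SAP 2.4 sentence and to the description of the primary model in SAP 2.5a.
- Replace the primary-analysis sentences in SAP Section 1 and Protocol 9.1 with the same model. In Protocol 9.1, confine the exploratory label to the interaction and subgroup work.
- Keep the components-only model as a labelled sensitivity analysis that plays no part in the p<0.10 rule.
- In SAP Section 1 and Protocol 9.1, restate the null-trial rule: arm 1's expected change is the covariate-standardised mean from the primary model (components at their arm 1 levels, covariates averaged over the intention-to-treat dataset), tested as a linear contrast at the 0.10 level already stated. Say that coding is 0/1.
- Date the change.

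The cost is wording in two documents. No new data are needed, and the sample size is unaffected.

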2.5. Secondary analyses

Purpose:

1. To evaluate interactions of treatments in the change of BP over 12 months.
2. To evaluate the pattern of change of BP over time.
3. To evaluate time from ED visit to arrival at first primary care visit (in days).
4. To evaluate attendance at two or more primary care visits within 12 months of randomization.

Methods/Approach: The following secondary analyses will be presented:

(a) Other analysis approaches on the primary measurement:

Additional analyses will include all the two-way interactions of the three intervention components (only considering interactions where at least one of the factors in the interaction demonstrates a sufficiently large main effect) added to the primary model in Section 2.4. Interactions between treatments will be assessed at $p=0.2$.

Since BP levels are captured at least weekly, we will also model BP (captured by text and in person visits) over time using a mixed effects model to see the pattern of blood pressure levels over time. The outcome of this longitudinal model will be BP levels over time (transformed if necessary), where the number of BP levels per person can vary. The fixed effects of the model include: the 3 main effects binary coded treatment predictors and the 3 stratification variables as specified in the primary analysis model. A random slope for a continuous time variable measured in days from randomization and a random intercept to allow subject specific heterogeneity in baseline BP and BP trajectories over time. We will assume compound symmetry for the covariance matrix but assess the appropriateness of this assumption using AIC and BIC compared to unstructured and autoregressive structures. We will also assess the significance of two-way interactions of treatments (only where at least one of the factors demonstrates a sufficiently large main effect) in this model at the 0.2 level. Mixed effects models are robust to data missing at random.

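### The components are defined 0/1, so in the models with treatment interactions their coefficients are low-level simple effects, not the main effects for which second-order power is stated

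*SAP*

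**What the plan says.** - **Label.** Protocol 9.1, SAP Section 1 (Analysis Plan) and SAP 2.4 all describe "main effect-coded binary predictors".
- **Definition.** Below the model equation, SAP 2.4 sets "HBtexts= 1 for daily healthy behavior texts and 0 for none; HighBPmonitor=1 if daily BP monitoring and 0 for weekly". Facilitated scheduling and transportation is also 1 or 0. The equation holds the three components and covariates, with no interactions.
- **Interactions.** SAP 2.5(a) has the two-way treatment interactions "added to the primary model in Section 2.4", provided at least one factor in the pair shows a large enough main effect. The longitudinal model in 2.5(a) and the exploratory models in 2.7 also allow treatment interactions.
- **Test levels.** SAP Section 1: "we will use an alpha level of 0.10 for all main effects and 0.20 for interactions". SAP 2.4: "Results will be reported as parameter estimates, 95% confidence intervals, and 2-sided p-values".
- **Power.** SAP Section 1: "For 80% power to detect the smallest main expected effect of 0.35 based on the Collins method", for a "3-factor experiment analyzed using a second order model (i.e. main effects and 2-way interactions), we require 196 subjects". It expects at least 240 completers. Protocol 9.3 equates the effect to 1 mm Hg with an SD of 2.8.
- **Selection.** Protocol 9.1 and SAP Section 1 take forward the combination with the largest expected SBP reduction, subject to significance at 0.10 (main effects) or 0.20 (interactions). If the trial is null overall, the arm 1 change is read from the intercept.

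**The concern.** In factorial work, effect coding usually means -1/+1 or -0.5/+0.5. With equal arms, a component's coefficient is then its effect averaged over the other components, whether or not interactions are in the model. With 0/1 coding this holds only while there are no interactions. Once they enter, the coefficient for healthy behavior texts is the effect of texts among participants with weekly prompts and no facilitation, and similarly for the other two components.

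The power statement names a second-order model, and the selection rule requires significant components in the very situation where interactions matter. Neither document says from which model the 0.10 component test is then taken. An analyst who read it from the printed coefficients of the 2.5(a) model would test a different quantity, less precisely, and could leave an active component out of the follow-on trial.

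**Working it through.** **Inputs.** Two-sided alpha 0.10, effect 0.35, N = 196 required and 240 expected (SAP Section 1 and 2.4); 1 mm Hg over SD 2.8, which is 0.357 (Protocol 9.3). Assumed here: eight equal arms, no covariates, no allowance for multiple imputation, residual SD scaled to 1.

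**1. The plan's own figure.** A main effect compares N/2 with N/2, so its variance is 4σ²/N. The number per level is 2(1.645 + 0.842)²/d².
- d = 1/2.8: 97 per level, 194 in total. The noncentral-t calculation with seven parameters gives exactly 196 (power 0.801).
- d = 0.35: 101 per level, 202 in total (204 by noncentral t).
- Power at N = 196, d = 0.35: Φ(0.35/√(4/196) − 1.645) = Φ(2.450 − 1.645) = 0.79.

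The stated 196 is reproduced, with the variance of a main effect.

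**2. Variance of the 0/1 coefficient.** Let α₁ be the main effect of component 1 under -0.5/+0.5 coding, and α₁₂ and α₁₃ its interactions. In the balanced design these estimates are uncorrelated, with variances 4σ²/N, 16σ²/N and 16σ²/N. The 0/1 coefficient is the effect with the others at their low level:

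b₁ = α₁ − α₁₂/2 − α₁₃/2

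- Both interactions in the model: Var(b₁) = (4 + 4 + 4)σ²/N = 12σ²/N, a factor of 3.
- One interaction: (4 + 4)σ²/N = 8σ²/N, a factor of 2.
- None: 4σ²/N, the same as effect coding.

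Inverting X'X for the eight cells gives the same values.

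**3. Which factor applies.** If one component passes the screen, both of its interactions enter. Its own term then carries the factor 3 and the other two the factor 2. If two or three pass, all three interactions enter and every term carries the factor 3. The SAP states no later removal of interactions.

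**4. Power at 0.10 two-sided, d = 0.35**, from Φ(0.35/√(4m/N) − 1.645):

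| Component term tested | m | N = 196 | N = 240 |
|---|---|---|---|
| Main-effects model, either coding | 1 | 0.79 | 0.86 |
| Second-order model, effect-coded | 1 | 0.79 | 0.86 |
| 0/1, one of its interactions in the model | 2 | 0.53 | 0.61 |
| 0/1, both of its interactions in the model | 3 | 0.41 | 0.47 |

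With d = 1/2.8, the m = 1 rows become 0.80 and 0.87, and the m = 3 row 0.42 and 0.48. A simulation of 20,000 trials with all three interactions fitted gave 0.412 (0/1) and 0.784 (effect-coded) at N = 196, and 0.461 and 0.854 at N = 240.

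The m = 2 and m = 3 rows take the simple effect to be 0.35. It equals the main effect only if there is no interaction.

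**The case against.** The strongest reply is that no prespecified test loses power. SAP 2.4 sets the 0.10 level for a model without interactions, where coding makes no difference. SAP 2.5(a) assigns a level (0.20) only to the interactions, and its screen presupposes that main effects have already been judged. Interaction tests and fitted arm means are the same under either coding, and the best combination is chosen on a fitted mean. Even in the 0/1 second-order model, the averaged main effect can be recovered as b₁ + b₁₂/2 + b₁₃/2, with variance 4σ²/N and about 79% power at N = 196. The label may simply mean main effects entered as binary variables, and reading arm 1 from the intercept fits 0/1 coding.

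All of this about the primary analysis stands. A reader might infer that the trial's 80% power falls to 41%, or that about 606 completers (3 × 202) are needed. The documents do not support either reading: the figure concerns a different estimand, in a model that the plan does not name as the source of the 0.10 tests.

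The reply does not settle the selection step. The plan neither specifies the recovering contrast nor says which model supplies the component test when interactions are significant. The intercept argument is also weak. The 2.4 equation includes sex, age, antihypertensive and race indicators, so its intercept is the arm 1 value only for men aged 18-64, not Black and not on antihypertensives. An overall arm 1 mean needs a contrast under either coding.

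**Conclusion.** The point holds as a gap in specification that is worth closing; it is not a loss of power in the primary analysis. The main-effects fit keeps about 79% power at 196 and 86% at 240. In 2.5(a), the longitudinal model and 2.7, a 0/1 component coefficient is no longer the main effect once its interactions enter. For the linear model on SBP change its variance is two or three times larger. Power would be about 41% at 196, or 47% at the 240 completers expected, only if the 0.10 test were read from a model containing both of that component's interactions and the simple effect were 0.35. The figures assume equal arms. With unequal loss, the effect-coded coefficient is only approximately unchanged when interactions are added.

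**What to change.** 1. In SAP 2.5(a) (including the longitudinal model) and 2.7, and wherever else treatment interactions enter, code the three components -0.5/+0.5. Make the label and the definitions in 2.4 agree.
2. State that the 0.10 component tests used for selection come from the main-effects model, or from the effect-coded second-order model.
3. Obtain the arm 1 mean and each combination's expected reduction as linear contrasts, at stated covariate values.
4. In 2.6, also centre the covariates that interact with components if main effects are to be read there. Recoding the components alone does not achieve this, because a component term would still refer to the covariates' reference categories.

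The cost is SAP wording and a recoding step, with no extra participants or data and no lost information. The one downside is that the intercept no longer represents arm 1, so the null-trial rule in Protocol 9.1 and SAP Section 1 must be reworded as a contrast.
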